### **6.5.3 Dose Modification Guidelines for TTI-621-related toxicities**

Please refer to Table 6-1 for dose delay and reduction recommendations for hematologic and non-hematologic toxicities. When the dose of TTI-621 is withheld based on the following criteria outlined below, clinical and laboratory re-evaluation should be repeated at least weekly or more frequently at investigator discretion following standard of care practice until the toxicity resolves to  $\leq$  Grade 1 or baseline or to a level assessed to be acceptable per [Section 6.5.1](#) and [Section 6.5.2](#) and/or by the investigator upon agreement from the medical monitor. Upon recovery, TTI-621 may be reinitiated either at the same dose level or at a reduced dose level. In events where there are transient lab value abnormalities that, based on investigator assessment, are not clinically significant or related to disease and not the study drug, continuation of therapy without following the dose modification guideline is permissible upon discussion with the sponsor medical monitor.

**Table 6-1: Dose Modifications for Dose 2 and Subsequent Doses**

Clinical Scenario	Action
Grade 3 thrombocytopenia or Grade 4 thrombocytopenia lasting $\leq$ 72 hours*	Continue TTI-621 at the same dose when the re-treatment criterion ( $\geq 75 \times 10^9/L$ or baseline) is met; no dose intensification until no occurrence of the same event at the re-challenge of the same dose (Part 3).
Grade 4 thrombocytopenia (platelet $<25 \times 10^9/L$ ) lasting $>72$ hours* or a platelet count $\leq 10 \times 10^9/L$ at any time	Delay TTI-621 dosing until the re-treatment criterion ( $\geq 75 \times 10^9/L$ or baseline) is met; transfuse platelet prophylactically against bleeding when platelet $<10K$ per ASCO practice guideline; Then resume TTI-621: 
 
• at the same dose if dose delay for 1 week;
 
• at a reduced dose by 1 dose level if dose delay for <math>> 1</math> week;
 
• at a reduced dose by 1 dose level if the event recurs
 
 Dose intensification can occur only when there is no occurrence of the same event upon re-dosing of TTI-621 at the same dose for two consecutive weeks. When dose reduction occurs, no further dose intensification will be allowed (Part 3).
$\geq$ Grade 3 thrombocytopenia (platelet $<50 \times 10^9/L$ ) with clinical bleeding (more than easily controlled epistaxis, mild gum bleeding or menses)	Delay TTI-621 dosing until the re-treatment criterion ( $\geq 75 \times 10^9/L$ or baseline) is met, and then resume TTI-621 at a reduced dose by 1 dose level. No further dose intensification (Part 3) will be allowed.
Grade 4 neutropenia (ANC $<500/\text{mm}^3$ ) lasting $>72$ hours* (unexplained by underlying disease)	Delay TTI-621 dosing when the re-treatment criterion (ANC $>1000/\text{mm}^3$ ) is met then resume TTI-621: 
 
• at the same dose if dose delay for 1 week
 
• at a reduced dose by 1 dose level if dose delay for <math>>1</math> week;
 
• at a reduced dose by 1 dose level if the event recurs
 
 Dose intensification (Part 3) can occur only when there is no occurrence of the same event upon re-dosing of TTI-621 at the same dose for two consecutive weeks. When dose reduction occurs, no further dose intensification will be allowed.
Grade 3 febrile neutropenia lasting $>72$ hours*; or Grade 3 neutropenia with any clinical evidence of infection; or Grade 4 febrile neutropenia	Delay TTI-621 dosing until the re-treatment criterion (ANC $>1000/\text{mm}^3$ ) is met, then resume TTI-621 at a reduced dose by 1 dose level. When dose reduction occurs, no further dose intensification will be allowed (Part 3).

Grade 3 infusion reaction (infusion reactions lasting up to 24 hours including fevers, rigors, headaches, hypotension, dyspnea, and urticaria related to TTI-621)	
The current infusion should be stopped promptly and standard care management administered. The medical monitor should be informed about the occurrence of the Gr3 event and one of the following options will be discussed following case-by-case assessment between the investigator and the medical monitor:
 
 
• Restarting the infusion after medical intervention and after the patient's condition has stabilized with additional supportive care medications,
 
• Terminating the current infusion, but re-challenging at the next weekly dose. At the re-challenge, the patient should receive premedication with corticosteroid per standard institution practice and/or established guidelines (Roselló et al., 2017); a slower rate of infusion and/or a lower dose of TTI-621 should be considered.
 
• Permanently discontinuing the study treatment. Do not intensify dose (Part 3)
 

Grade 4 infusion reaction (anaphylaxis or other life-threatening reactions lasting more than 24 hours)	Permanently discontinue TTI-621

Grade 3 or greater non-hematologic toxicity related to TTI-621 with the following exceptions:
 
 
• Grade 3 nausea and/or vomiting lasting <72 hours with standard supportive care
 
• Transient Grade 3 fatigue lasting <math>\leq</math>72 hours
 
• Transient asymptomatic Grade 3 laboratory abnormalities that last <72 hours with standard supportive care and considered not clinically significant following agreement between investigators and the sponsor or designees.
 
	
For Grade 3 events, delay TTI-621 dosing until the re-treatment criteria is met, then resume TTI-621 at a reduced dose by 1 dose level.
 
No dose reduction is required for the exceptions listed.
 
For Grade 4 events, discontinuation of TTI-621 should be considered. If, per investigator's assessment, it is in the patient's best interest to continue the treatment, TTI-621 treatment can be resumed when the AE resolves to a level that meets the re-treatment criteria
 
Do not intensify dose (Part 3)

Grade 3 or greater non-hematologic toxicity NOT related to TTI-621	Investigator's discretion to withhold or decrease dose of TTI-621. Do not intensify dose of TTI-621 until the resolution of the AEs to Grade 1, baseline, or a level (must be $\leq$ Grade 2) determined to be acceptable per investigator assessment (Part 3)

Grade 3 anemia	
Delay TTI-621 dosing until resolution to <math>\leq</math> Grade 1 or baseline, then resume TTI-621 treatment:
 
 
• at the same dose if dose delay for 1 week;
 
• at a reduced dose by 1 dose level if dose delay for <math>> 1</math> week;
 
• at a reduced dose by 1 dose level if the event recurs
 
• Dose intensification can occur only when there is no occurrence of the same event upon re-dosing of TTI-621 at the same dose for two consecutive weeks. When dose reduction occurs, no further dose intensification will be allowed (Part 3).
 

Grade 4 anemia	
Discontinuation of TTI-622 should be considered. If it is in the patient's best interest to continue TTI-622 per investigator assessment, withhold dose until resolved to <math>\leq</math> Grade 1 or baseline, then reduce by 1 dose level.

\* When Grade 4 thrombocytopenia, Grade 4 neutropenia, or Grade 3 febrile neutropenia is first observed, hematology labs need to be repeated before the next scheduled visit to allow assessment of whether the event lasts for  $> 72$  hours and additionally as clinically indicated per investigator discretion following standard institutional practice.

#### 6.5.4 Intrasubject Dose Intensification (Phase 1b dose expansion Part 3)

For phase 1b Part 3, intrasubject dose intensification will be as follows:

**Newly enrolled subjects:** Dose intensification will start at Week 3 for subjects when the prior TTI-621 dose was associated with Grade 2 or lower treatment-related AEs. From Week 3 to Week 8, subsequent weekly doses of TTI-621 will be increased in 0.1 mg/kg/week increments as tolerated (Grade 2 or lower treatment-related AEs) and not to exceed a maximum dose of 0.5 mg/kg/week. After Week 9, additional dose intensification is not permitted.

**Previously enrolled subjects:** For previously enrolled subjects, dose intensification up to a maximum of 0.5 mg/kg/ week is at the investigator's discretion and should start at Week 3 if the prior TTI-621 dose was associated with Grade 2 or lower treatment-related AEs. More guidance on when to dose intensify in occurrence of AEs is provided in Table 6-1.

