## 1.7 Anticipated or Possible Risks in Human Subjects

### *Summary of Dose-Escalation Safety Data*

Data from the first 18 subjects enrolled in the dose-escalation phase of the study show that TTI-621 has been reasonably well tolerated. Transient, dose-dependent decreases in platelets without clinical sequelae occurred in the hours following infusion in the majority of subjects exposed to TTI-621. Thrombocytopenia was relatively brief with recovery to baseline platelet counts by the next weekly dose and appeared attenuated with weekly TTI-621 exposure. Other Grade 3/4 cytopenias (monocytes, neutrophils, and lymphocytes) were also frequently observed; all were transient and resolved without sequelae.

The majority of subjects experienced mild to moderate infusion-related reactions (IRRs) that typically occurred after the first TTI-621 infusion only. IRRs were reported across all dose cohorts with no obvious dose relationship and occurred despite premedication with an antihistamine and acetaminophen.

Three subjects experienced reversible Grade 3 hypophosphatemia in the days following their first infusion of TTI-621. Hypophosphatemia in 1 of the 3 subjects was considered related to TTI-621 and was therefore reported as a DLT. The event rapidly resolved without intervention. Hypophosphatemia was considered unrelated to TTI-621 in the other 2 subjects and their phosphate levels were corrected by oral phosphate.

No subjects in either the 0.05 mg/kg/week or 0.1 mg/kg/week dose groups experienced dose-limiting toxicity (DLT). However DLTs were reported for 2 of 5 subjects treated at the 0.3 mg/kg/week dose: 1 subject with Grade 4 thrombocytopenia and 1 subject with Grade 4 thrombocytopenia and Grade 3 elevated alanine aminotransferase/aspartate aminotransferase (ALT/AST). Upon review of cumulative adverse events (AEs) and laboratory values, the Safety Review Committee (SRC) recommended proceeding with

enrollment at an intermediate dose level of 0.2 mg/kg TTI-621 (Cohort 2a), and to dose reduce all subjects participating in the 0.3 mg/kg cohort to the 0.2 mg/kg dose level (one subject was dose reduced to the 0.1 mg/kg dose level).

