### 6.4.1 TTI-621 Monotherapy

#### Phase 1b – Part 2 and Part 3

Subjects enrolled in these cohorts will receive a starting dose of 0.2 mg/kg/week TTI-621. For Part 3, intrasubject TTI-621 dose-intensification is required for newly enrolled subjects. All subjects will receive a dose ramp-up regimen which includes initial two-weeks of 0.2 mg/kg treatment followed by intrasubject dose intensification at an increment of 0.1 mg/kg per week up to 0.5 mg/kg within 5-8 weeks. Details regarding when dose intensification should be delayed or stopped due to AEs are provided in [Section 6.5.3](#).

#### Phase 1b Dose Optimization - Part 4

Subjects in the phase 1b dose optimization phase (Part 4) will undergo dose escalation of TTI-621, starting with Level 1 (dose of 0.5 mg/kg) per dose escalation plan (See [Table 3-4](#), [Section 3.3.2](#)) given once weekly. Following a 3+3 escalation design and using a revised DLT criteria, enrollment will continue through Level 2 (starting dose of 0.7 mg/kg), Level 3 (starting dose of 1.0 mg/kg) and Level 4 (starting dose of 1.4 mg/kg) respectively. In the starting dose cohort (0.5 mg/kg), the first 3 patients will be treated sequentially to allow close monitoring of toxicity and timely dose adjustment if needed. The second and third patient will not start the study treatment until the first and second patient, respectively, have completed the initial 2 weeks of study treatment and had no observation of TEAEs meeting DLT criteria. If a DLT is noted in Level 1, there may be de-escalation to Cohort 0 (priming dose of 0.2 mg/kg at week 1 followed by 0.5 mg/kg at subsequent doses) with progression through Levels 2, 3 and 4 using the dose priming approach of 0.2 mg/kg at week 1 followed by the respective level dose regimens at subsequent weeks.

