## 7.6 TTI-621 Intrasubject Dose Intensification – Additional Assessments Every Week of Dose Intensification (only applicable to Part 3)

For subjects who are dose intensified at Week 3 through Week 8, the following assessments are required on Day 1, only if not already part of the scheduled weekly visit. For the TTI-621 monotherapy cohorts, assessments will be performed at the indicated time relative to infusion of TTI-621. For subjects in the combination cohorts, pre-infusion assessments will be performed relative to the start of the combination partner infusion, as applicable.

- serum for PK at end of infusion and 4 hours after Time 0 (see [Table 7-2](#))
- whole blood for receptor occupancy: pre-infusion and at end of infusion (approximately 60 minutes after Time 0,  $\pm$  15 minutes)
- hematology at 4 hours after Time 0. Additional hematologic monitoring should be instituted at the discretion of the treating Investigator.
- serum chemistries at 4 hours after Time 0

## 7.7 Week 4

On Day 1 of Week 4 (Day 22 of treatment), the below tests and observations will be performed. For the TTI-621 monotherapy cohorts, assessments will be performed at the indicated time relative to the infusion of TTI-621. For subjects in the combination cohorts, assessments will be performed relative to the infusion of the combination partner, as applicable. All of these assessments can be performed up to 24 hours pre-infusion, with the exception of vital signs and PK. For Part 3 only, if intrasubject dose intensification occurs at this visit please also refer to [Section 7.6](#) for additional assessments.

- symptom driven physical examination and ECOG score
- body weight
- vital signs prior to infusion and at completion of infusion (60 minutes after Time 0 [ $\pm$  15 minutes]). For subjects in the combination cohorts, the latter timepoint (60 minutes after Time 0) is to be done only if the combination partner and TTI-621 are administered more than 60 minutes apart; performed per the institutional standard of care. For subjects under Part 4 vitals are not required at end of infusion. Refer to [Appendix D. Table 2](#).
- urine or serum pregnancy test for women of childbearing potential
- Serum for PK:
  - For Part 3: serum for PK trough levels (pre-dose)
  - For Part 4: serum for PK trough levels (pre-dose). If a priming regimen is used see [Appendix F](#) for revised sampling timepoints.
- Hematology:

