## 7.8 Week 5-7

On Day 1 of Week 5, the below tests and observations will be performed. For the TTI-621 monotherapy cohorts, assessments will be performed at the indicated time relative to the infusion of TTI-621. For subjects in the combination cohorts, assessments will be performed relative to infusion of the combination partner, as applicable. All assessments can be performed up to 24 hours pre-infusion, with the exception of PK. For Part 3 only, if intrasubject dose intensification occurs at this visit please also refer to [Section 7.6](#) for additional assessments.

- symptom driven physical examination and ECOG score
- vital signs, performed per the institutional standard of care
- body weight
- Part 3 and Part 4: hematology (results must be available prior to study drug). For Part 4, if a priming dose is required see [Appendix F](#).
- Part 3 and Part 4: serum for PK trough levels (pre-dose). For Part 4, if a priming dose is required see [Appendix F](#).
- AEs
- concomitant medications

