Pregnancy test (women of childbearing potential)	X (serum)					pre (serum or urine)				pre (serum or urine)		pre Wk 12 then Q4 wks (serum or urine)				
Hematology	X	pre	1 hr, (EOI) 2 hr, 4 hr	pre	pre	pre	pre	pre	pre	pre		4 hr	X	X		
	WBC with automated 5-part differential, hemoglobin, RBC, absolute reticulocytes, platelets															
Serum chemistries	X	pre		pre	pre	pre				pre		pre Wk 12 then Q4 wks	4 hr	X	X	
	Alkaline phosphatase, albumin, ALT, AST, bilirubin (direct, indirect, and total), BUN, creatinine, glucose, LDH, total protein, uric acid, and electrolytes (sodium, potassium, calcium, chloride, bicarbonate, phosphorus)															
TSH (for Nivolumab combination only)	X											pre Wk12 + Q12 wks		X	X	
Coagulation panel	X													X		
	Prothrombin time, partial thromboplastin time, INR, fibrinogen															
Urinalysis		pre								pre				X		
	Including color, appearance, specific gravity, pH, glucose, bilirubin, ketones, occult blood, and protein															
	D = Day; Post = after start of TTI-621 infusion; EOT = end of treatment visit; SFU = safety follow-up visit; LTFU = long term safety follow-up visit; EOI = end of infusion (1 hr)															

Assessments	≤ -D14	W1 D 1 Pre a	W1 D1 Post	W2 D1	W3 D1	W4 D1	W5 D1	W6 D1	W7 D1	W8 D1 Pre	W8 D1 Post	W9+ D1	Intra Sub Dose g Intens	EOT	SFU e	LTFU
Dose Intensification Weeks for phase 1b Part 3 (see Section 6.5.4)																
		Except where otherwise noted pre-dose assessments can be performed up to 24 hours pre-infusion (see also Section 7). All scheduled treatment days have a window of ±2 days.												≤1 Wk j	± 2D	Q4 (±1 wk)
Central Laboratory Assessments																
PK		pre	1 hr (EOI) 2hr, 4hr, D2	pre	1 hr (EOI) 2 hr, 4 hr D2, D4	pre Wk 9, 10, 11, 12, 13, 14, 15 & 16	1 hr (EOI), 4 hr	X								
Cyto/Chemokine		pre	1 hr (EOI) 4 hr	pre						pre	1 hr (EOI), 4 hr, D2	pre Wk 9		X		
ADA		pre				pre				pre		pre Wk 12 then Q4 wks		X	X	X f
TCR Vβ p		pre								pre		pre Wk 16				
Anti-Tumor Antibodies		pre										pre Wk 16				
Peripheral Receptor Occupancy (blood) l		pre	1 hr (EOI)	pre						pre	1 hr (EOI)	pre Wk 9	pre, 1 hr (EOI)			
Receptor Occupancy (bone marrow) p	pre n									pre n						
Innate and Adaptive Response Assay		pre								pre					X	

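### Part 3 dose steps at Weeks 5-7 depend on related AEs of Grade 2 or lower, but no pre-dose serum chemistry is scheduled in those weeks

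*Protocol*

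**What the plan says.** **The condition for a step.** Protocol 6.5.4 sets the first step: "Dose intensification will start at Week 3 for subjects when the prior TTI-621 dose was associated with Grade 2 or lower treatment-related AEs". For the following weeks, "subsequent weekly doses of TTI-621 will be increased in 0.1 mg/kg/week increments as tolerated (Grade 2 or lower treatment-related AEs"), up to a ceiling of 0.5 mg/kg/week. Table 6-1 separately bars intensification after related non-hematologic toxicity of Grade 3 or more, apart from listed exceptions. Section 6.5.2 requires other related toxicity to have settled before any dose, also with exceptions. Under Section 9, a laboratory abnormality that is treated or judged clinically relevant is reported as an AE.

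**The pace.** Section 6.4.1 describes "dose intensification at an increment of 0.1 mg/kg per week up to 0.5 mg/kg within 5-8 weeks".

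**The chemistry schedule.** Sections 7.2, 7.4, 7.5, 7.7 and 7.9 list serum chemistries at Weeks 1, 2, 3, 4 and 8. Section 7.8 covers Weeks 5-7 and opens with "On Day 1 of Week 5, the below tests and observations will be performed"; its list contains no chemistry. Appendix D Table 1 agrees: the chemistry row is blank at Weeks 5, 6 and 7, and after Week 8 it reads "pre Wk 12 then Q4 wks". In weeks when the dose is raised, Section 7.6 adds "serum chemistries at 4 hours after Time 0", Time 0 being the start of the infusion.

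**Hematology, by contrast.** Section 7.8 requires "Part 3 and Part 4: hematology (results must be available prior to study drug").

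**The concern.** The condition looks back at what the prior dose did. For blood counts, the schedule supplies a current result before every dose. For chemistry it does so at Weeks 3, 4 and 8 but stops at Weeks 5-7, where the uninterrupted ramp takes its last step. The sample added in intensification weeks cannot inform the step made that day, because it is drawn after the raised dose has been given. It can only inform the next one.

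The protocol's own experience shows why the timing matters. Section 1.7 reports: "Three subjects experienced reversible Grade 3 hypophosphatemia in the days following their first infusion of TTI-621". One of these events was judged related and was a DLT. A further DLT subject, at 0.3 mg/kg, had Grade 3 ALT/AST elevation. An abnormality that develops over days and causes no symptoms could be absent at 4 hours and give no clinical prompt before the next visit. A site following the schedule exactly could then raise the dose after an undetected Grade 3 chemistry event. Evaluating the safety of individual dose intensification is part of the primary objective for Parts 2 and 3 (Section 2.2).

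**Working it through.** **1. Reproduce the stated pace.** Inputs from 6.4.1 and 6.5.4: start 0.2 mg/kg, ceiling 0.5 mg/kg, increment 0.1 mg/kg, first step at Week 3, last permitted step at Week 8.

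- Number of steps = (0.5 − 0.2) / 0.1 = 3.
- Earliest week at the ceiling = 3 + 3 − 1 = Week 5; latest = Week 8.

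This matches the stated 5-8 weeks.

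**2. Set the laboratory schedule against the step weeks** (7.5 to 7.9, Appendix D Table 1).

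| Week | Pre-dose hematology | Pre-dose chemistry | Chemistry at 4 h |
|---|---|---|---|
| 3 | yes | yes | if dose raised |
| 4 | yes | yes | if dose raised |
| 5 | yes | no | if dose raised |
| 6 | yes | no | if dose raised |
| 7 | yes | no | if dose raised |
| 8 | yes | yes | if dose raised |

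**3. Uninterrupted ramp.**

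- Week 3, 0.2 to 0.3: pre-dose chemistry is scheduled and falls after the Week 2 dose.
- Week 4, 0.3 to 0.4: pre-dose chemistry is scheduled and falls after the Week 3 dose.
- Week 5, 0.4 to 0.5: no pre-dose chemistry. The only chemistry after the 0.4 mg/kg dose is the Week 4 sample at 4 hours. The nominal time from that sample to the Week 5 infusion is 7 × 24 − 4 = 164 hours, just under 7 days.

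**4. Delayed ramps.** Three steps can be placed in Weeks 3-8 in C(6,3) = 20 ways. If the last step falls in week m, the other two lie in Weeks 3 to m − 1, giving C(m − 3, 2) placements. The week before the last step is itself a step week in m − 4 of them.

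| Week of step to 0.5 mg/kg | Placements | Pre-dose chemistry | 4-h sample after prior dose | No 4-h sample after prior dose |
|---|---|---|---|---|
| 5 | 1 | no | 1 | 0 |
| 6 | 3 | no | 2 | 1 |
| 7 | 6 | no | 3 | 3 |
| 8 | 10 | yes | 4 | 6 |

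The step to the maximum lacks pre-dose chemistry in 1 + 3 + 6 = 10 of 20 placements. In 1 + 2 + 3 = 6 of those there is a 4-hour sample after the prior dose. In 0 + 1 + 3 = 4 there is no scheduled chemistry after the prior dose, because the dose was not raised in the preceding week (Week 5 or 6) and Section 7.6 did not apply. The 10 placements ending at Week 8 have pre-dose chemistry.

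These are counts of possible paths. The documents give no frequencies of delay, so they are not probabilities. The 4 paths assume that the prior dose was repeated unchanged. If it was withheld for toxicity, 6.5.3 calls for laboratory re-evaluation at least weekly.

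**The case against.** The strongest reply is that this is a monitoring choice and not a contradiction. Sections 6.5.4, 7.6, 7.8 and Appendix D Table 1 can all be followed as written. The condition is worded in AE grades and names no laboratory test. AEs and hematology are reviewed at every visit, and a chemistry sample follows every raised dose. Appendix D Table 1 allows additional assessments when clinically indicated, and Section 9.5 asks for close monitoring of liver enzymes. The retreatment rule in 6.5.2 applies to every dose, yet chemistry is only four-weekly from Week 12, so that rule alone cannot imply weekly chemistry.

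The risk evidence is also modest. The hypophosphatemia followed the first infusion, an interval that Week 2 pre-dose chemistry covers. Two of the three events were judged unrelated, and the related one resolved quickly without intervention. No onset time is given for the ALT/AST event. Among 46 subjects intensified at investigator discretion (Section 1.8.3), every related event of Grade 3 or more seen in at least 2 patients was hematologic. Table 6-1 and 6.5.2 also exempt some transient, asymptomatic Grade 3 laboratory abnormalities.

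Most of this stands and limits the point. A reader might infer that the step is taken without any of the laboratory data that the condition needs. That is not supported: hematology is in hand, and on the uninterrupted ramp one chemistry result follows the prior dose. A reader might also infer that late-detected events would be tabulated under the wrong dose. SAP 3.5 summarizes Part 3 safety by monotherapy or combination therapy, not by dose at onset, so no planned table would change.

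What does not stand is reliance on discretionary testing. A mandatory condition on AE grade is not met reliably for asymptomatic chemistry changes when the test is left to clinical prompting. The argument from four-weekly chemistry after Week 12 does not reach Weeks 5-7 either, because those are weeks in which the dose may still be rising.

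**Conclusion.** The point holds for chemistry and for Weeks 5-7 only. A step in those weeks, including the Week 5 step to 0.5 mg/kg on the uninterrupted ramp, rests for chemistry on at most a 4-hour sample after the prior dose, and on none if the dose was not raised the week before. Steps at Weeks 3, 4 and 8 have scheduled pre-dose chemistry. Coverage at Weeks 6 and 7 is not uniform: 5 of the 9 placements ending there have the 4-hour sample and 4 do not.

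The conclusion rests on two readings of the protocol: that chemistry abnormalities can be AEs that count toward the condition (Section 9), and that the listed assessments are the scheduled minimum. It assumes no particular event rate. The documents do not show that a chemistry event was missed, and the intensification data they report suggest that such events are uncommon. The mismatch is modest but worth correcting, because the same schedule already handles hematology consistently.

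**What to change.** Reconcile 6.5.2, 6.5.4 and Table 6-1 with 7.6, 7.8 and Appendix D Table 1, so that the schedule supplies the chemistry information that the step condition relies on before a Week 5-7 step. Keep the existing 4-hour sample: it is the only post-dose chemistry scheduled in intensification weeks, and substituting another draw for it would lose that information. How the sections are aligned is for the sponsor and investigators to settle. This point takes no position on the dose, the increment or the toxicity threshold.

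The cost is an edit to the assessment schedule and at most one additional local chemistry panel per affected visit, drawn with the pre-dose hematology already required. Three visits (Weeks 5, 6 and 7) could be affected, so the most is three panels per subject. On the uninterrupted ramp only the Week 5 visit carries a step, so one panel would suffice.
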